11.2.3 Laboratory Assessments

All clinical safety laboratory tests listed in the section below will be performed at local laboratories. Subject eligibility will be determined based on the baseline laboratory results.

Clinically significant laboratory test abnormalities will be followed until resolution or stabilization and the overall clinical outcome has been ascertained (See [Section 11.4.5](#)).

11.2.3.1 Blood Sample Collection for General Clinical Laboratory Assessments

Blood samples will be collected and reviewed for the following clinical laboratory tests within 72 hours of C1D1 (or on C1D1 prior to dosing):

- Serum Chemistry: Glucose, Blood Urea Nitrogen (or Urea), Creatinine, Sodium, Potassium, Chloride, Calcium, Magnesium, Phosphorus, Total Protein, Albumin, Total Bilirubin, Alkaline Phosphatase, alanine aminotransferase (ALT), aspartate aminotransferase (AST), Gamma-Glutamyltransferase, and Lactate Dehydrogenase. Bicarbonate (or total CO₂) is optional.
- Hematology: White Blood Cell Count, Red Blood Cell Count, Hemoglobin, Hematocrit, Platelet Count, Neutrophils, Lymphocytes, Monocytes, Eosinophils, Basophils

- Coagulation profile: activated partial thromboplastin time (APTT), prothrombin time/international normalized ratio (PT/INR)

11.2.3.2 Urinalysis

Macroscopic assessment of the amount of protein, glucose, white blood cells and blood will be conducted. If abnormalities are noted, these will be recorded, and a microscopic analysis conducted and recorded. If at any time, the subject's serum creatinine is \geq Grade 2, then a serum chemistry, microscopic urinalysis including the measurement of protein, glucose, blood, white blood cells will be conducted. If abnormalities are noted, then spot urine sodium, protein and creatinine should be performed to assess fractional sodium excretion (plasma creatinine x urine sodium / plasma sodium x urine creatinine) and urine protein/creatinine ratio (urine protein mg/urine creatinine mg ratio).

11.2.3.3 Pregnancy Testing

Pregnancy testing will be performed in females of child-bearing potential and testing may be performed on urine or serum. If a positive urine pregnancy test is obtained, a confirmatory serum pregnancy test should be conducted. If confirmatory test is positive, subject must terminate tipifarnib treatment immediately and follow pregnancy reporting guidelines outlined in the protocol.

Female subjects enrolled in AIM-HN must have a negative serum or urine pregnancy test within 72 hours prior to start of study medication (Cycle 1 Day 1). Pregnancy assessments will be performed on Day 1 of each cycle starting at Cycle 2.

11.3 Adverse Event Reporting

11.3.1 Procedure for Reporting Adverse Events

The AE reporting period for safety surveillance begins when the subject is included into the study (date of first signature of AIM-HN informed consent) and continues through the study's post-treatment follow-up period, defined as approximately 30 days from the final administration of the study treatment or immediately before initiation of any other anticancer therapy, whichever comes first.

The Investigator is required to grade the severity/intensity of each AE. Investigators will reference the NCI-CTCAE v 5.0. This is a descriptive terminology that can be used for AE reporting. A general grading (severity/intensity) scale is provided at the beginning of the referenced document, and specific event grades are also provided. If a particular AE's severity/intensity is not specifically graded by the guidance document, the Investigator is to revert to the general definitions of Grade 1 through Grade 5 and use his or her best medical judgment.

The 5 general grades are:

- Grade 1: Mild

- Grade 2: Moderate
- Grade 3: Severe or disabling
- Grade 4: Life-threatening
- Grade 5: Death related to AE. Note: Death (Grade 5 as defined by NCI-CTCAE version 5.0) is mainly regarded as an outcome, to be documented as described below.

According to the Sponsor's convention, if a severity/intensity of Grade 4 or 5 is applied to an AE, then the Investigator must also report the event as an SAE as per [Section 11.4.2](#). However, a laboratory abnormality with a severity/intensity of Grade 4, such as low white blood cell count or increased ALT, is considered serious only if the condition meets one of the serious criteria described below.

In the case of death, the primary cause of death (the event leading to death) should be recorded and reported as an SAE. "Fatal" will be recorded as the outcome of this respective event; death will not be recorded as separate event. Only if no cause of death can be reported (e.g., sudden death, unexplained death), the death per se might be reported as an SAE.

Investigators must also systematically assess the causal relationship of AEs to the IP. Decisive factors for the assessment of causal relationship of an AE to the study treatments include, but may not be limited to, temporal relationship between the AE and the study treatments, known side effects of the study treatments, medical history, concomitant medications and procedures, course of the underlying disease and study procedures.

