11.4 Definitions

11.4.1 Adverse Events

An AE is any untoward medical occurrence in a patient or clinical investigation subject administered a pharmaceutical product, which does not necessarily have a causal relationship with this treatment. An AE can therefore be any unfavorable and unintended sign (including an abnormal laboratory finding), symptom, or disease temporally associated with the use of a medicinal product, whether or not considered related to the medicinal product. In cases of surgical or diagnostic procedures, the condition/illness leading to such a procedure is considered as the AE rather than the procedure itself. In case of a fatality, the cause of death is considered as the AE, and the death is considered as its outcome.

Relatedness of an AE will be evaluated as follows:

- Not related: Not suspected to be reasonably related to the IPs. AE could not medically (pharmacologically/clinically) be attributed to the IPs under study in this clinical study protocol. A reasonable alternative explanation must be available.

- Related: Suspected to be reasonably related to the IPs. AE could medically (pharmacologically/clinically) be attributed to the IPs under study in this clinical study protocol.

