11.4.4 Events Not to Be Considered as AEs/SAEs

Medical conditions present at the initial study visit that do not worsen in severity or frequency during the study are defined as Baseline Medical Conditions and are NOT to be considered AEs. Progression of underlying disease is not an AE and therefore not an SAE per se, rather an efficacy endpoint, unless deemed to be causally related to administration of IP. However, if

adverse signs or symptoms occur in association with disease progression then these should be recorded as AEs and reported as SAEs if meeting any seriousness criteria.

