### 9.8.1 Adverse Events

All summaries of AEs will be based on treatment-emergent AEs (TEAEs) unless otherwise indicated.

TEAE is defined as AE that starts on or after the first dose of the study drug and within 30 days of the last administration of the study drug.

Counting of AEs will be by subject, not by event; subjects will be counted only once within each SOC or PT.

The count and percentage of subjects who report TEAEs will be summarized for AIM-HN safety analysis set as follows:

TEAEs by SOC and PT

TEAEs by PT (Any Grade and Grade  $\geq$  3)

TEAEs by SOC, PT, and maximum NCI-CTCAE grade

Serious TEAEs by SOC and PT

TEAEs related to tipifarnib by PT (Any Grade and Grade  $\geq$  3)

TEAEs related to tipifarnib by SOC, PT, and maximum NCI-CTCAE grade

Serious TEAEs related to tipifarnib by SOC and PT

TEAEs leading to discontinuation of tipifarnib by SOC and PT

TEAEs with an outcome of death by SOC and PT

Non-Serious TEAE experienced by  $\geq$  5% of subjects by PT

For grade summaries, subjects with multiple events within a particular SOC or PT will be counted under the category of their most severe event within that SOC or PT. Events will be sorted by descending frequency by SOC, and by PT within SOC for summaries.

AEs will be listed for individual subjects, including information regarding onset, duration, severity, seriousness, outcome and relationship to study drug.

AEs will not be summarized by Cycle, except for Overall Summary and AEs by SOC and PT for Cycle 1.

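### Protocol 11.3.1 and 11.4.1 conflict with 11.4.4 on a death in the AE reporting period from unrelated HNSCC progression, and the SAP's all-causality fatal TEAE table inherits the ambiguity

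*Protocol*

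**What the plan says.** Three parts of Protocol section 11 bear on how a death from the cancer is recorded.

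- **11.3.1:** "In the case of death, the primary cause of death (the event leading to death) should be recorded and reported as an SAE". The event's outcome is then fatal. The only special case is a death for which no cause can be given.
- **11.4.1**, within the AE definition: "In case of a fatality, the cause of death is considered as the AE, and the death is considered as its outcome".
- **11.4.4:** "Progression of underlying disease is not an AE and therefore not an SAE per se, rather an efficacy endpoint", with an exception for progression judged to be caused by the drug. It adds a rule for clinical manifestations of progression: "adverse signs or symptoms occur in association with disease progression then these should be recorded as AEs and reported as SAEs if meeting any seriousness". Section 11.4.2 lists a fatal result among the criteria that make an event serious.

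The AE reporting period runs from AIM-HN consent to the close of safety surveillance after treatment, which is "defined as approximately 30 days from the final administration of the study treatment or immediately before initiation of any other anticancer therapy"; the earlier of the two applies (11.3.1).

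SAP 9.8.1 sets the tabulation window by start date alone: "TEAE is defined as AE that starts on or after the first dose of the study drug and within 30 days of the last administration". Its planned outputs include serious TEAEs by SOC and PT and "TEAEs with an outcome of death by SOC and PT". It does not exclude, recode or separately display progression terms. SAP 9.8.2 separately tabulates and lists deaths with their causes, taken from the survival status CRF.

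**The concern.** Consider a subject who stops tipifarnib for progression and dies 20 days later, before any new therapy, with unrelated HNSCC progression given as the primary cause. Under 11.3.1 and 11.4.1 that cause is a fatal SAE. Under 11.4.4 it is not an AE. None of these sections refers to another on this case.

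The same kind of death could therefore be a fatal TEAE at one site and absent from the AE data at another. AIM-HN is single-arm, so no concurrent rate shows how much of a fatal or serious TEAE figure comes from the underlying cancer. The reading also decides whether the 24-hour SAE report in Protocol 11.3.2 is due.

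**Working it through.** **No planned figure to reproduce.** Neither document states an expected fatal or serious TEAE rate. The check is a comparison of the rules, followed by an illustration of scale.

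**1. Rules compared for deaths in the AE reporting period**

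| Recorded primary cause of death | 11.3.1 and 11.4.1 | 11.4.4 | Conflict? |
|---|---|---|---|
| Event unrelated to progression | Fatal SAE | Not addressed | No |
| Specific fatal sign or symptom of progression | Fatal SAE | SAE, because fatal | No |
| Progression judged caused by the drug | Fatal SAE | Exempted from the exclusion | No |
| Progression alone, unrelated to the drug | Fatal SAE | Not an AE or SAE | **Yes** |

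Only the last row is contradictory.

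**2. Outputs affected**

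- All-causality fatal TEAE table (SAP 9.8.1): affected directly.
- All-causality serious TEAE table (SAP 9.8.1): affected less, because subjects are counted once and one who already has another serious TEAE does not change the overall rate.
- Drug-related TEAE and serious TEAE tables (SAP 9.8.1): not affected, because unrelated progression enters neither under either rule.
- Deaths by cause (SAP 9.8.2): not affected, because the source is the survival status CRF.

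**3. Effect per death.** Take N = 80, the planned minimum for the per-protocol set (Protocol synopsis); the actual safety set may differ. One reclassified death moves the fatal TEAE rate by 1/80 = 1.25 points. It moves the serious TEAE rate by 0 or 1.25 points.

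Contribution of k such deaths to the fatal TEAE rate, with exact (Clopper-Pearson) 95% intervals:

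| k | If 11.4.4 governs | If 11.3.1 and 11.4.1 govern |
|---|---|---|
| 4 | 0% (0 to 4.5%) | 5.0% (1.4 to 12.3%) |
| 8 | 0% (0 to 4.5%) | 10.0% (4.4 to 18.8%) |
| 16 | 0% (0 to 4.5%) | 20.0% (11.9 to 30.4%) |

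The values of k are chosen to show scale and are not forecasts.

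**4. Illustration of how many deaths might be involved.** Inputs:

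- Median overall survival m = 5 to 8 months. Protocol 4.3 gives this for second-line systemic therapy, not for tipifarnib or for time after its last dose.
- Constant hazard (assumed).
- A full 30-day window after last dose for all 80 subjects (assumed).
- 50% to 90% of those deaths recorded as unrelated progression (assumed; not in the documents).

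Probability of death in 30 days, with the SAP's 30.4375 days per month:

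p = 1 − exp(−ln 2 × (30/30.4375) / m)

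- m = 8: p = 8.2%, and 80 × 0.0819 = 6.5 deaths.
- m = 5: p = 12.8%, and 80 × 0.1277 = 10.2 deaths.

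Applying the assumed share:

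- Lowest: 6.5 × 0.5 = 3.3 subjects, or 4.1 points.
- Highest: 10.2 × 0.9 = 9.2 subjects, or 11.5 points.

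These figures compare every site following one rule with every site following the other; mixed practice would move the rate less. Deaths on treatment would add to the count. New anticancer therapy started within 30 days would shorten the reporting period and reduce it.

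**The case against.** The strongest reply is that the sections can usually be followed together. Section 11.3.1 asks for the event leading to death, and 11.4.4 requires serious signs and symptoms of progression to be reported. A site that names the terminal clinical event satisfies every section. This stands, and it confines the conflict to deaths where progression itself is the recorded cause. It does not remove the conflict, because 11.3.1 asks for the primary cause and a site may reasonably give progression.

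Second, the SAP has other protection. Serious and fatal tables are by PT, so a reported progression term would show as its own row, and SAP 9.8.2 gives all deaths with causes. This also stands. However, a reader can discount a reported term but cannot see from the TEAE tables which deaths were left out, and no reconciliation with the survival status CRF is planned.

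Third, Protocol 11.2 refers to eCRF completion conventions and 11.3.2 to SAE form instructions. Either may settle the matter. Neither is among the documents, so differing practice between sites is possible but not shown.

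A reader might also infer more than the documents support:

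- **That every death is affected.** SAE reporting covers the reporting period only, and three of the four rows above show no conflict.
- **That the safety tables become uninterpretable.** The drug-related tables and total deaths by cause do not depend on the reading.
- **That IDMB decisions are distorted.** Protocol 6.7.2 lists observed safety as a ground for stopping, but no stopping rule visible in the documents uses a fatal TEAE rate, and 11.1 has the IDMB review all relevant safety data.

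**Conclusion.** The contradiction is real but narrow. It concerns a death within the AE reporting period whose primary cause is recorded as HNSCC progression unrelated to tipifarnib. For that death the protocol gives two incompatible instructions and no order of precedence, and the SAP does not settle how it is tabulated. The all-causality fatal TEAE table is exposed, and the serious TEAE table less so. The primary ORR analysis is untouched.

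The size cannot be derived from the documents. The 1.25 points per death is arithmetic at N = 80. The range of about 3 to 9 subjects, or roughly 4 to 11.5 points, is an illustration that depends on the constant hazard, on survival under other therapies and on the assumed 50% to 90% share. It should not be quoted as an estimate for this trial.

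**What to change.** **Protocol.** Reconcile 11.3.1 and 11.4.1 with 11.4.4 so that one stated rule covers death from unrelated progression, with a cross-reference between the sections. Which direction to take is for the sponsor and is not proposed here. The cost is an amendment with IRB/IEC approval (Protocol 4.5 and 13.1). Because SAP section 3 reports early closure of the study, this would change few further reports.

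**SAP 9.8.1 and 9.8.2.** This is the more useful part.

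- Present serious and fatal TEAEs twice, with and without disease-progression terms, using a term list fixed before database lock. The version without those terms is then largely independent of the rule a site followed.
- Reconcile fatal TEAEs with survival status CRF deaths: for each death in the TEAE window, show whether a fatal TEAE was recorded and under which term. This also exposes the remaining variation between sites that name a symptom and sites that name progression.

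The cost is a term list, two repeated tables and the reconciliation. No new data are needed.

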11.3.2 Procedure for Reporting Serious Adverse Events

In the event of any new SAE occurring during the reporting period, the Investigator must immediately (i.e. within a maximum of 24 HOURS after becoming aware of the event) inform the person(s) identified in the Serious Adverse Event Report Form by telephone, by fax or by email. When an event (or follow-up information) is reported by telephone, a written report must be sent immediately thereafter by fax or e-mail. Reporting procedures and timelines are the same for any new information on a previously reported SAE. For names, addresses, telephone and fax numbers for SAE reporting, see information included in the Serious Adverse Event Report Form. All written reports should be transmitted using the Serious Adverse Event Report Form, which must be completed by the Investigator following specific completion instructions.

The AE section of the eCRF must be completed and a copy of the information transmitted with the Serious Adverse Event Report Form. Other relevant pages from the eCRF may also be provided (e.g. medical history, concomitant drugs). The Investigator/Reporter must respond to any request for follow-up information (e.g. additional information, outcome and final evaluation, specific records where needed) or to any question the Sponsor may have on the SAE within the same timelines as described for initial reports. This is necessary to permit a prompt assessment of the event by the Sponsor to allow for strict regulatory timelines associated with expedited safety reporting obligations.

11.3.3 Safety Reporting to Health Authorities, Institutional Review Boards and Investigators

The Sponsor will send appropriate safety notifications to Health Authorities in accordance with applicable laws and regulations. The Investigator must comply with any applicable site-specific requirements related to the reporting of SAEs (and in particular deaths) involving his/her subjects to the IRB/IEC that approved the study.

In accordance with ICH GCP guidelines, the Sponsor will inform the Investigator of “findings that could adversely affect the safety of subjects, impact the conduct of the study or alter the IRB/IEC’s approval/favorable opinion to continue the study.” In particular and in line with respective regulations, the Sponsor will inform the Investigator of AEs that are both serious and unexpected and are considered to be related to the administered product (“suspected unexpected serious adverse reactions”, SUSARs). The Sponsor will also provide SUSAR information to the Competent Authorities in all Member States concerned and Ethics Committees in compliance with SUSAR reporting outlined in the European Directive 2001/20/EC. The Investigator should place copies of safety reports in the Investigator Site File. National regulations with regards to safety reporting notifications to investigators will be taken into account. When specifically required by regulations and guidelines, the Sponsor will provide appropriate safety reports directly to the concerned lead IRB/IEC and to the Competent Authorities in all Member States concerned and will maintain records of these notifications. When direct reporting by the Sponsor is not clearly defined by national or site-specific regulations, the Investigator will be responsible for promptly notifying the concerned IRB/IEC of any safety reports provided by the Sponsor and of filing copies of all related correspondence in the Investigator Site File.

11.4 Definitions

11.4.1 Adverse Events

An AE is any untoward medical occurrence in a patient or clinical investigation subject administered a pharmaceutical product, which does not necessarily have a causal relationship with this treatment. An AE can therefore be any unfavorable and unintended sign (including an abnormal laboratory finding), symptom, or disease temporally associated with the use of a medicinal product, whether or not considered related to the medicinal product. In cases of surgical or diagnostic procedures, the condition/illness leading to such a procedure is considered as the AE rather than the procedure itself. In case of a fatality, the cause of death is considered as the AE, and the death is considered as its outcome.

Relatedness of an AE will be evaluated as follows:

- Not related: Not suspected to be reasonably related to the IPs. AE could not medically (pharmacologically/clinically) be attributed to the IPs under study in this clinical study protocol. A reasonable alternative explanation must be available.

- Related: Suspected to be reasonably related to the IPs. AE could medically (pharmacologically/clinically) be attributed to the IPs under study in this clinical study protocol.

11.4.2 Serious Adverse Event

An SAE is any untoward medical occurrence that at any dose:

- Results in death.
- Is life-threatening. NOTE: The term “life-threatening” in this definition refers to an event in which the subject is at risk of death at the time of the event; it does not refer to an event that hypothetically might cause death if it were more severe.
- Requires inpatient hospitalization or prolongation of existing hospitalization.
- Results in persistent or significant disability/incapacity.
- Is a congenital anomaly/birth defect.
- Is otherwise considered as medically important.

Important medical events that may not result in death, be life-threatening, or require hospitalization may be considered as SAEs when, based upon appropriate medical judgment, they may jeopardize the subject or may require medical or surgical intervention to prevent one of the outcomes listed in this definition. Examples of such events include allergic bronchospasm requiring intensive treatment in an emergency room or at home, blood dyscrasias or convulsions that do not result in subject hospitalization, or the development of drug dependency or drug abuse.

For the purposes of reporting, any suspected transmission of an infectious agent via an IP is also considered a serious adverse reaction and all such cases should be reported in an expedited manner.

11.4.3 Events that Do Not Meet the Definition of an SAE

Elective hospitalizations to administer, or to simplify study treatment or study procedures (e.g. an overnight stay to facilitate chemotherapy and related hydration therapy application) are not considered as SAEs. However, all events leading to unplanned hospitalizations or unplanned prolongation of an elective hospitalization (e.g. undesirable effects of any administered treatment) must be documented and reported as SAEs.

